11.0 DESCRIPTION OF STUDY TREATMENT

11.1 Study Drug Description

SB623 cells are provided as a 1-mL sterile cell suspension, containing $\geq 5 \times 10^6$ cells/mL, cryopreserved in CryoStoreTM freezing media.

11.2 Study Drug Packaging

Individual 1.5-mL Nalgene[™] cryovials.

11.3 Study Drug Shipment and Storage

The cryovials containing the frozen cell suspensions are shipped in a dry nitrogen shipper and should be stored in the vapor phase within the shipping container provided by the Sponsor until transferred at the site to a GMP-compliant liquid nitrogen container.

The Sponsor will arrange for Study Drug to be shipped to the clinical site.

11.4 Preparation and Administration

Details for preparation of the cell suspension for administration will be provided by the Sponsor. Clinical sites will be provided necessary materials for reconstitution of the cells and will be trained by the Sponsor. The cryopreserved cells will be thawed, washed, centrifuged, and re-suspended in Plasma-Lyte A at varying concentrations (see Section 4.1) for administration to the patient within approximately 3 hours of re-suspension. Prior to administration, a gram stain and a test for endotoxin will be done and a sterility test initiated on the last cell wash to insure continued sterility. If the endotoxin level is > 5 EU/mL or the gram stain is positive, implantation will not occur. If the sterility test is positive, an investigation will be conducted to determine the source of the contamination. In addition, identification of the pathogen and sensitivity will be done and the patient treated with an appropriate antibiotic. In this event, the patient will be followed closely for adverse events associated with a possible infection and response to antimicrobial therapy, including frequent clinic visits until any infection is cleared.

This Investigational Product may not be used for any purpose other than this clinical study.

11.5 Study Drug Accountability Procedures

The Investigator will be responsible for maintaining inventory and accounting for all Study Drug received from the Sponsor on a drug accountability log. After reconciliation has been completed, all Study Drug vials received by the Investigator (used and unused) will be collected, and the used vials destroyed at the site under supervision of the monitor per institutional standard operating procedure. Unopened vials will be kept frozen until returned to the Sponsor.

12.0 CONCOMITANT MEDICATIONS

All concomitant medications including prescription and over-the-counter drugs taken during the 14 days prior to enrollment or used anytime during the study through 2 years post Study Drug will be documented. Documentation (through month 9 only) will include changes from the prior visit, start and stop dates, dose, and reasons for the medication use.

Investigational drugs or devices for any other indication are not allowed during the study.

13.0 STUDY WITHDRAWAL/TERMINATION

13.1 Study Termination

The protocol may be terminated at anytime by the Sponsor in the event of significant Study-Drug-related adverse effects.

13.2 Site Termination

The study site will be closed if there is evidence of fraud, other unethical conduct, or significant non-compliance to the protocol or to Good Clinical Practices (GCPs). Should patient enrollment be unsatisfactory, or data recording be inaccurate and/or incomplete, the Sponsor may terminate the study and remove all study materials from the study site.

13.3 Patient Discontinuation

Patients will be free to discontinue from the study at any time without giving a reason(s). Patients will be considered discontinued from the study in the event of any of the following reasons:

- Withdrawal of the patient's consent for any reason
- Investigator's discretion due to patient's medical condition

If patient withdrawal occurs during the study period, the Last Evaluation visit should be performed, whenever possible, at the time of patient withdrawal or as soon as possible (see Section 10.8). The Investigator should continue to evaluate the medical condition of any patient who has withdrawn for 2 years post-implant.

In the event a patient withdraws from the study for any reason, the Investigator must notify the Principal Monitor by telephone within 24 hours of withdrawal.

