1.0 PROTOCOL SYNOPSIS

Protocol #:	SB-STR01
Title:	A Phase 1/2A Study of the Safety and Efficacy of Modified Stromal Cells (SB623) in Patients with Stable Ischemic Stroke
Study Objectives:	Primary : To evaluate the safety and tolerability of intracranial administration of SB623 cells. Safety will be determined during 2 years post-implant.
	Secondary: To evaluate clinical and radiographic response to 3 dose levels of intracranial administration of SB623 cells. The major efficacy endpoints will be determined at 6 months; measures will also be at 1, 2, 3, 4, 9, 12, and 24 months.
Background and Rationale	SB623 cells are adult bone-marrow-derived cells that have been transiently transfected with a plasmid construct encoding the intracellular domain of human Notch-1. SB623 cells secrete factors that protect neurons in models of ischemic insult. In a rat occlusion model of stroke to the middle cerebral artery region, implantation of SB623 into and around the area of the infarct resulted in improvement of neurological behavior.
	The safety of implanted SB623 cells was evaluated in a 6-month primate study and in 2 nude rat studies (4 mos. and 12 mos.). The primates were immunosuppressed with cyclosporine and the nude rats further immunosuppressed with an anti-NK cell antibody. There were no SB623-related clinical, laboratory, or histological abnormalities found.
	The stereotactic surgical delivery of cells to patients with stroke has been shown to have an acceptable safety profile in two prior clinical studies with another product. In addition, a retrospective study of over 2,650 patients undergoing stereotactic surgery during a 28-year period at one major clinic has shown a high degree of safety with the procedure.
	Finally, the European Stroke Scale (ESS), the Modified Rankin Score, the National Institute of Health Stroke Scale (NIHSS), the Fugl-Meyer scale for motor function, and a neurocognitive battery (e.g. , Rey Complex Figure Test), have been used and validated, at least for acute stroke. Fluorodeoxyglucose positron emission tomography (FDG-PET) imaging has shown that changes in metabolic activity relative to baseline in the infarct area and surrounding areas correlated with performance on the motor subscale of the ESS.

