Study Design	This is an open-label safety study of stereotactic, intracranial injection of SB623 cells in patients with hemiparesis from stable ischemic stroke who have remained stable during the prior 3 weeks (based on NIHSS assessments at weeks -3 and -1). While primarily a safety study, efficacy parameters will also be evaluated. Three cohorts will receive escalating single doses of SB623, which are to be stereotactically implanted into grey or white matter sites adjacent to the infarct region. One burr-hole craniostomy will be created, and cells implanted using 3 needle tracks with 5 deposits for each track at varying depths around the damaged area. Cell

	implantation will be standardized as to volume (20 μ L/denosit) and rate (10
	implantation will be standardized as to volume ($20 \mu L/deposit$) and rate ($10 \mu L/min$), with spacing between each implant of approximately 5-6 mm. Each deposit is expected to take approximately 2-3 minutes, with each needle track being completed within 15 minutes. Each cohort will consist of 6 subjects defined by an increasing total number of cells implanted. Safety will be monitored by the Investigator, Principal Monitor, Medical Monitor, and an external Data Safety Monitoring Board. For the first cohort, a single patient will first be dosed, then evaluated over a 2 week period for safety prior to dosing the next member of the cohort. This 2- week interval will continue between each of the remaining members of this cohort. If the safety profile is acceptable for a cohort, and after review by the DSMB, the first patient in each subsequent cohort will be dosed, beginning 4 weeks after dosing of the last patient of the prior cohort. For the second and third patients in each of the subsequent cohorts, there will be an interval of 2 weeks after the prior patients prior to further enrollment.
	Safety will be monitored by clinical symptoms, laboratory findings, and MRI brain imaging. Two or more serious adverse events will trigger a review by the DSMB before continuing enrollment. Possible efficacy will be determined based on changes in the clinical measures of stroke through standardized assessments and on FDG-PET brain imaging.

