10.10 Last Evaluation (End of Month 24 ±14 Days or Early Withdrawal)

- Physical Exam.
- Vital Signs Including Weight
- Hematology (Section 15.3)
- Serum Chemistry (Section 15.3)
- Lipid Panel
- Plasma Cytokines (Section 15.3)
- Imaging (head MRI & PET)
- Clinical Stroke Evaluations
- Cognitive Questionnaire (Section 23.0, Table 7)
- Blood for antibodies to SB623 and peripheral blood mononuclear cells (PBMC) function assays and for storage of PBMCs (Section 15.7)
- Luminex assay for antibodies to SB623 and PBMC function assay
- Adverse Events
- Concomitant Medications (see Section 12.0)

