18.4 Analysis of Safety

Adverse events, clinical laboratory data, and vital signs will be analyzed to evaluate the safety of SB623 for all patients in the Safety population through 2 years after the dose of Study Drug.

A treatment-emergent adverse event will be defined as any event not present prior to the initiation of treatment or any event already present that worsens in either intensity or frequency following exposure to study treatment.

All adverse event data will be listed per patient including severity, relationship to Study Drug, and action taken. Frequency within each treatment group of each type of adverse event will be summarized using an acceptable coding dictionary.

Laboratory data and vital signs will be listed by patient. Laboratory data values above and below normal ranges which are considered clinically significant will be indicated on the listing. Descriptive statistics will be displayed for each laboratory parameter and vital sign assessment at each time point. The mean change from baseline in each of these continuous variables will also be described.

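### Protocol 13.3 asks for 2-year evaluation of withdrawn patients but gives it no visits, data capture or analysis, so late harms in patients discontinued for their medical condition can go unrecorded

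*Protocol*

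**What the plan says.** **Objective and horizon.** The protocol synopsis states: "Safety will be determined during 2 years post-implant". Protocol 18.4 analyses safety "for all patients in the Safety population through 2 years after the dose of Study Drug", and SAP 7.4 uses the same 2-year horizon.

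**Treatment.** "Three cohorts will receive escalating single doses of SB623". After Day 1 there is no study treatment left to stop.

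**Discontinuation.** Protocol 13.3 gives two reasons for being considered discontinued from the study: withdrawal of consent, and "Investigator's discretion due to patient's medical condition". Both lead to the same steps. First, "the Last Evaluation visit should be performed, whenever possible, at the time of patient withdrawal or as soon as possible (see Section 10.8"). Then "The Investigator should continue to evaluate the medical condition of any patient who has withdrawn for 2 years post-implant".

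**The visit itself.** Protocol 10.10 is headed "Last Evaluation (End of Month 24 ±14 Days or Early Withdrawal") and lists the procedures for that one visit. Table 4 shows it as the last column, at Month 24, and does not mention early withdrawal. Section 10.8, which 13.3 cites, is the Month 6 visit.

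**Analysis.** The Safety population is every treated patient with any post-baseline data (protocol 18.2.2, SAP 4.2). SAP 7.1.2 uses available data without imputation unless otherwise specified. The only later imputation rules, in the SAP addendum, concern Fugl-Meyer items. The SAP does not mention data collected after withdrawal.

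**Reporting windows.** Protocol 16.2 ends the AE reporting period 24 weeks after SB623, whereas SAP 7.4.1 ends it at 24 months. Protocol 16.5 requires immediate SAE reporting from the dose to 4 weeks afterwards.

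**The concern.** In a trial of continuing treatment, discontinuation for medical condition usually means stopping the drug. Here it can only mean stopping study participation. The trigger is the patient's health, so the patients affected may be those in whom late harm is most likely. Losing their scheduled AE enquiry, MRI and stroke scales would be loss of data that depends on the outcome, and it would bear on the primary objective in only 18 patients.

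The sentence in 13.3 on continued evaluation shows that the authors foresaw this. But it is a recommendation that names no assessments, timing, form or analysis. It also covers patients who withdrew consent and patients the investigator discontinued in the same terms, although what may be collected can differ between them. Whether anything from those months reaches the 2-year safety tables is left to each site.

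**Working it through.** **1. What happens to a discontinued patient's safety data.**

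| Data | Provision | Covered after discontinuation? |
|---|---|---|
| AEs recorded before discontinuation | Protocol 16.2 and 16.6: followed until they resolve or stabilise | Yes |
| AEs that cause discontinuation | SAP 7.4.1: own summary and listing | Yes |
| Unresolved Grade 2 event judged possibly related or more | Protocol 9.2: participation is extended | Yes, for that event |
| Membership of the denominator | Protocol 18.2.2, SAP 4.2 | Yes |
| New AEs after the Last Evaluation | Protocol 13.3: general evaluation to 2 years | No visit, CRF entry or analysis specified |
| New MRI changes | SAP 7.4.2: recorded on the CRF at follow-up visits, details then reported as an AE | No visit is scheduled, so no route into the data |

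The gap is confined to the last two rows. A patient in the denominator with no recorded late event is counted as having had none.

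**2. How much scheduled observation is involved.** Take a patient discontinued just after the Month 3 visit, a timing assumed for illustration. Table 4 still has visits at Months 4, 6, 9, 12 and 24, all with MRI and stroke scales. One Last Evaluation replaces five visits, and 24 - 3 = 21 months pass without scheduled assessment. Those months are not free of follow-up, because 13.3 still asks for evaluation.

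**3. The plan's own safety figure.** Protocol 18.5 and SAP 3.3 state a chance below 5% of missing a dose-limiting toxicity (DLT) with 6 patients and a true rate of 40%. With n = 6 and p = 0.40, P(0 events) = (1 - p)^n = 0.6^6 = 0.0467, so the figure reproduces. It assumes all six are fully observed. If one or two patients contributed nothing, it would be 0.6^5 = 7.8% or 0.6^4 = 13.0%. These are outer bounds. No DLT observation window is defined, and early DLTs would be seen before most withdrawals.

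**4. Effect on a 2-year event rate (illustration).** Assumption: k of 18 treated patients are discontinued for their condition, each later has a serious event, and none is captured. The documents give no rate for any of these steps, so k = 1 to 3 is shown. Intervals are Clopper-Pearson 95%: lower limit = Beta quantile at 0.025 with parameters (k, 18 - k + 1); upper limit = Beta quantile at 0.975 with parameters (k + 1, 18 - k). For zero events the upper limit is 1 - 0.025^(1/18) = 0.185.

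| k | With capture | Without capture |
|---|---|---|
| 1 | 1/18 = 5.6% (0.1-27.3%) | 0/18 (0-18.5%) |
| 2 | 2/18 = 11.1% (1.4-34.7%) | 0/18 (0-18.5%) |
| 3 | 3/18 = 16.7% (3.6-41.4%) | 0/18 (0-18.5%) |

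The denominator is 18 throughout, because the Safety population keeps discontinued patients.

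**The case against.** The strongest reply is that 13.3 already contains the remedy. A reader might infer that 10.10 and 13.3 contradict each other, with one ending follow-up at early withdrawal and the other continuing it. The text does not support that: 10.10 lists the procedures of a single visit and does not forbid anything after it, Table 4 says nothing about early withdrawal, and 13.3 describes a sequence of visit first, continued evaluation after. This part of the objection stands.

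It also stands that a patient who is doing badly is not invisible. The deterioration that leads to discontinuation should already be a recorded AE, is followed, and appears among AEs leading to discontinuation. Withdrawals are notified within 24 hours, and the DSMB reviews toxicity continuously.

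A reader might also infer that these patients drop out of the safety analysis, and compare 2/18 with 0 of 16 completers (95% CI 0-20.6%). No completers-only safety analysis is planned, and even patients lost to follow-up remain in the analysis (protocol 13.4).

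Whether the consent form addresses follow-up after withdrawal cannot be judged from the public copy, which omits it.

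What the objection does not answer is new late events. Following recorded AEs does not detect new ones, keeping a patient in the denominator creates no data, and a general duty to evaluate, with no form or analysis behind it, does not fill a safety table. The reporting windows in protocol 16.2 and 16.5 offer no reliable back-up for late events in any patient.

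**Conclusion.** The point holds as a gap between a stated duty and the means to carry it out. Investigator discontinuation for medical condition ends scheduled safety assessment for a reason that may be related to harm, in a single-dose study whose primary objective is 2-year safety. What can be lost is new AEs and MRI changes after withdrawal, and the error would make late safety look better than it was.

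The size is not known. The change from 11% to 0% with two missed events rests on three assumptions: that patients are discontinued for their condition, that they later have new events, and that the 13.3 evaluation fails to bring those events into the database. The documents do not show that any such loss happened or was likely. With 18 patients even one or two missed events would matter to the reading of the result, so the point merits an amendment. It does not undermine the safety design as a whole.

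**What to change.** - **Protocol 13.3:** separate withdrawal of consent from investigator discontinuation. Patients who still consent remain in study follow-up to Month 24 on the existing Table 4 safety assessments (AEs and SAEs, MRI, stroke scales), as far as the investigator judges feasible. After consent withdrawal, collect only what consent allows, and say what that is.
- **Data capture and analysis:** enter these data on the CRF, and state in SAP 7.4 that they are included in the 2-year safety analysis.
- **Cross-reference:** in 13.3, change 10.8 to 10.10 for the Last Evaluation.
- **Windows:** reconcile the AE period (24 weeks in protocol 16.2, 24 months in SAP 7.4.1) and the 4-week SAE window in protocol 16.5 with the 2-year objective. This affects all 18 patients, not only those who withdraw.

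**Cost.** The assessments are already scheduled for every patient, so no new procedure is added. There is some extra follow-up effort for discontinued patients, and the change is a protocol amendment that needs ethics committee or IRB approval under protocol 19.5, with a matching SAP edit.

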13.4 Patients Lost to Follow Up

Patients who cannot be reached after at least three attempts will be categorized as lost to follow up. The attempts to reach the patients must be documented, with at least one of the attempts written and sent to the patient via certified mail. Patients lost to follow up will still be included in the analysis of the study.

14.0 STOPPING RULES

A dose-limiting toxicity will be defined as any grade 3 or 4 events which are at least possibly related to study product or administration procedure. If the first patient in a cohort has a dose-limiting toxicity attributable to the SB623 cells, then no further patients will be dosed in that cohort until a comprehensive evaluation has been conducted. If 2 of 6 patients in a cohort have a dose-limiting toxicity attributable to the SB623 cells, then no further patients will be dosed in that or higher-dose cohorts. Each dose-limiting-toxicity will be evaluated by the DSMB.

In addition, adverse events attributable to the surgical procedure, such as intracranial infection, intracranial bleeding, or seizures, shall be subject to review by the DSMB

The DSMB shall be the final arbitrator for attributions.

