9.0 INVESTIGATIONAL PLAN

9.1 Overall Study Design

This is an open-label study of stereotactic, intracranial injection of SB623 cells (SB623 cells) in patients with hemiparesis from stable ischemic stroke who have remained stable during the

prior 3 weeks (as documented by NIHSS assessments at weeks -3 and -1). Three cohorts will receive escalating singe doses of SB623, which are to be stereotactically implanted into grey or white matter sites adjacent to the infarct region. One burr-hole craniostomy will be created, and cells implanted using 3 needle tracks with 5 cell deposits for each track at varying depths. Cell implantation will be standardized as to volume (20 uL/deposit) and rate $(10 \,\mu L/min)$, with spacing between each implant of approximately 5-6 mm. Each deposit is expected to take approximately 2-3 minutes, with each needle track being completed within 15 minutes. Each cohort will consist of 6 subjects defined by an increasing total number of cells implanted. Safety will be monitored by the Investigator, Principal Monitor, Medical Monitor, and an external Data Safety Monitoring Board (DSMB). For the first cohort, a single patient will first be dosed, then evaluated over a 2 week period for safety prior to dosing the next member of this cohort. This 2-week interval will continue between each of the remaining members of the cohort. If the safety profile is acceptable for a cohort, and after review by the DSMB, the first patient in each subsequent, sequential cohort will be dosed, beginning 4 weeks after dosing of the last patient of the prior cohort. For the second and third patients in each of the subsequent cohorts, there will be an interval of 2 weeks after the prior patients prior to further enrollment.

Safety will be monitored by clinical symptoms, laboratory findings, and MRI brain imaging. Efficacy will be determined based on changes in the clinical measures of stroke and on FDG-PET brain imaging.

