3. STUDY DESIGN

3.1 OVERVIEW

This is an open-label safety study of stereotactic, intracranial injection of SB623 cells in patients with hemiparesis from stable ischemic stroke who have remained stable during the prior 3 weeks (based on NIHSS assessments at weeks -3 and -1). While primarily a safety study, efficacy parameters will also be evaluated. Three cohorts will receive escalating singe doses of SB623, which are to be stereotactically implanted into grey or white matter sites adjacent to the infarct region. One burr-hole craniostomy will be created, and cells implanted using 3 needle tracks with 5 cell deposits for each track at varying depths around the damaged area. Cell implantation will be standardized as to volume (20 μ L/deposit) and rate (10 μ L/min), with spacing between each implant of approximately 5-6 mm. Each deposit is expected to take approximately 2-3 minutes, with each needle track being completed within 15 minutes. Each cohort will consist of 6 patients defined by an increasing total number of cells implanted. Safety will be monitored by the Investigator, Principal Monitor, Medical Monitor, and an external Data Safety Monitoring Board (DSMB). For the first cohort, a single patient will first be dosed, then evaluated over a 2 week period for safety prior to dosing the next member of the cohort. This 2-week interval will continue between each of the remaining members of the cohort. If the safety profile is acceptable for a cohort, and after review by the DSMB, the first patient in each subsequent cohort will be dosed, beginning 4 weeks after dosing of the last patient of the prior cohort. For the second and third patients in each of the subsequent cohorts, there will be an interval of 2 weeks after the prior patients prior to further enrollment.

SanBio Incorporated Protocol SB-STR01

A dose-limiting toxicity (DLT) will be defined as any grade 3 or 4 events which are at least possibly related to study product or administration procedure. If the first patient in a cohort has a DLT attributable to the SB623 cells, then no further patients will be dosed in that cohort until a comprehensive evaluation has been conducted. If 2 of 6 patients in a cohort have a DLT attributable to the SB623 cells, then no further patients will be dosed in that or other higher-dose cohorts. Each DLT will be evaluated by the DSMB. The DSMB shall be the final arbitrator for attributions.

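### The first-patient hold in section 14.0 counts only cell-attributed DLTs, so when a serious procedural DLT in a cohort's first patient is the first SAE, no protocol or SAP text makes the next implant wait for the DSMB

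*Protocol*

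**What the plan says.** Protocol section 14.0 defines a DLT as "any grade 3 or 4 events which are at least possibly related to study product or administration procedure". The procedure is therefore inside the definition.

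Both dosing consequences are narrower. The hold begins "If the first patient in a cohort has a dose-limiting toxicity attributable to the SB623 cells", and the permanent stop at 2 of 6 patients has the same restriction. The synopsis and section 9.1 repeat the rule, and SAP 3.1 has it as "If the first patient in a cohort has a DLT attributable to the SB623 cells".

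Procedural events are not left out of DSMB oversight. Section 14.0 adds "Each dose-limiting-toxicity will be evaluated by the DSMB" and "adverse events attributable to the surgical procedure, such as intracranial infection, intracranial bleeding, or seizures, shall be subject to review by the DSMB", and closes with "The DSMB shall be the final arbitrator for attributions". None of these sentences says when the review must be complete or that dosing waits for it.

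Section 9.1 sets the pace of dosing. The first patient of cohort 1 is dosed, "then evaluated over a 2 week period for safety prior to dosing the next member of this cohort", and the 2-week spacing continues through that cohort. For the second and third patients of later cohorts, "there will be an interval of 2 weeks after the prior patients prior to further enrollment".

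Two provisions do put DSMB review ahead of further dosing regardless of attribution. The synopsis and SAP 7.6 require it once there are two or more SAEs. Section 9.1 and SAP 7.6 require it before the first patient of each later cohort.

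**The concern.** The hold depends on attribution to the cells, and the DSMB has the final say on attribution. Until it has spoken, nobody knows whether the hold applies. Every patient receives cells and surgery together and there is no sham arm, so a seizure or new deficit after implantation may be hard to assign.

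The protocol's background shows that such a question can stay open. Section 2.2.3 describes a five-patient trial of intrastriatal cell implants that was terminated after one cortical vein occlusion, and says that attribution remained unresolved.

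The case is clearest for the first patient of cohort 1. Section 3.8 says SB623 has not been studied clinically before, so no earlier SAE can exist, and unless that patient has two SAEs the two-SAE rule cannot apply. The second person ever to receive the product could be implanted while the DSMB is still considering what happened to the first.

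**Working it through.** **Which events qualify.** Table 6 (Appendix C) grades seizures as Grade 4, so a seizure at least possibly related to the procedure is a DLT. A bleed alone may not be: the haemorrhage row grades units transfused, so an intracranial bleed would usually qualify through a Grade 3-4 neurological deficit.

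**What happens after one serious procedural DLT**

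| Situation | Does any text make the next implant wait for the DSMB? |
|---|---|
| First SAE, in the first patient of a cohort | No |
| Second or later SAE | Yes: two-SAE rule (synopsis, SAP 7.6) |
| Last patient of cohort 1 or 2 | Yes: cohort-boundary review (section 9.1, SAP 7.6) |

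The remaining safeguards do not change the first row. The cohort 1 safety evaluation names no event that stops dosing. SAE reporting within 24 hours (section 16.5) leads to a sponsor evaluation that may, but need not, end in suspension.

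**The plan's own figure.** Section 18.5 puts the chance of missing a DLT at under 5% with 6 patients and a true rate of 40%. This reproduces: 0.6^6 = 0.0467. It does not depend on the hold and needs no change.

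**How often the first row could arise.** Let p be the chance per patient of a serious procedural DLT. Assume independence, one SAE per patient, and no other SAEs.

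*Study-wide SAE count.* The event must be the trial's first SAE and fall in the first patient of cohort 1, 2 or 3, with 0, 6 or 12 event-free patients before it. These cases are mutually exclusive, so the chance is p[1 + (1-p)^6 + (1-p)^12].

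*Per-cohort SAE count.* A single event in any of the three first patients qualifies, so the chance is 1-(1-p)^3.

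| p | Study-wide count | Per-cohort count |
|---|---|---|
| 1% | 0.01 × (1 + 0.941 + 0.886) = 2.8% | 3.0% |
| 5% | 0.05 × (1 + 0.735 + 0.540) = 11.4% | 14% |
| 10% | 0.10 × (1 + 0.531 + 0.282) = 18.1% | 27% |
| 20% | 0.20 × (1 + 0.262 + 0.069) = 26.6% | 49% |

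The documents do not say which count applies.

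**Where the rates come from.** Section 2.2.4 gives complications below 1% in over 2,650 stereotactic operations. The four listed rates sum to 0.36 + 0.36 + 0.08 + 0.08 = 0.88%. The 5%, 10% and 20% rates are assumptions. The 20% equals the 1 in 5 of the terminated trial (exact 95% CI 0.5% to 72%), which used different cells and had unresolved attribution.

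**Delay if a hold is added.** Expected first-patient holds are at most 3p. At an assumed 2 to 4 weeks each, that is 0.06-0.12 weeks at 1%, 0.3-0.6 at 5%, 0.6-1.2 at 10% and 1.2-2.4 at 20%. Section 9.1 implies at least 10 + 4 + 4 + 4 + 4 = 26 weeks of enrolment: five 2-week gaps in cohort 1, 4 weeks before each later cohort, and two 2-week gaps in each, with patients 4 to 6 dosed without further spacing.

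**The case against.** The rule can be defended. Cell-dose stopping rules properly count cell-attributed toxicity, because the procedure is the same at every dose (section 4.1). Section 14.0 has a separate paragraph sending surgical events to the DSMB. The DSMB is final arbitrator, so an investigator's procedural rating does not settle that the hold is inapplicable. SAP 7.6 says the DSMB's procedures are in its charter, which may fix the timing of review. The event is also rare at the surgical rates cited. The two human-cell trials in section 2.2.3, with 12 and 14 implanted patients and procedures reported as well tolerated, are closer comparators than the porcine-cell trial behind the 20% rate; section 7.0 cites the second as a source for the present surgery.

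Most of this stands and limits the point. The permanent stop at 2 of 6 should stay as it is, and the higher rates are illustrations. What does not stand is that oversight alone supplies a hold. Being final arbitrator does not oblige the DSMB to rule before the next dose. A charter could add a safeguard, but the protocol's own rule would still restrict the hold to cell-attributed events.

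Two stronger readings are tempting. A reader might infer that procedural DLTs escape the DSMB, or that nothing ever requires DSMB review before dosing resumes after one. The documents support neither: every DLT is evaluated, and the two-SAE rule and the cohort-boundary review are real holds whatever the attribution.

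**Conclusion.** The point holds in a narrow form. A single serious procedural DLT in a cohort's first patient, when it is the first SAE, carries no mandatory hold pending the DSMB's evaluation in either document.

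The chance of meeting that situation is about 3% at a 1% rate. At assumed rates of 5% to 20% it is about 11% to 27% on a study-wide SAE count, and up to 49% if the count is per cohort. SAEs unrelated to the procedure would lower the study-wide figures. All the figures include cases where the DSMB finishes within the 2 weeks and no harm follows. They therefore should not be read as the chance that a patient is implanted before the review is complete, and the documents do not show that this happened.

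The case for change rests on the consequence in a first-in-human intracranial study and on the low cost, more than on frequency. The unseen charter is the main remaining uncertainty.

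**What to change.** Keep the cell-attributed hold and the 2-of-6 stop. In section 14.0, section 9.1, the synopsis and SAP 3.1, add: *if the first patient in a cohort has a DLT that is also an SAE, whether rated to the cells or to the procedure, no further patient is dosed until the DSMB has completed its evaluation and recommended whether to continue.* The release condition should be the recommendation and not certainty about the cause, so that the hold cannot become open-ended.

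Limiting the addition to serious events keeps out ordinary postoperative pain, since Table 6 makes regular narcotic use Grade 4.

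Repeat the existing two-SAE rule in section 14.0, where it is now absent. A separate hold for two patients with serious procedural DLTs is not needed, because that rule largely covers it.

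The cost is wording in four places, a matching line in the DSMB charter, and an occasional temporary hold. No extra data are needed. The 2 to 4 weeks assumed per hold is not a figure from the documents.
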